9.2. Secondary Efficacy

9.2.1. Secondary Efficacy Endpoints

The secondary efficacy endpoints include the following:

- Patient Global Impression of Change (PGIC)

- EDSS
- TNmAS – Total Limbs (TL)

9.2.2. Secondary Efficacy Analyses

Secondary efficacy endpoints will be summarized descriptively and analyzed using the same type of MMRM analysis used for the co-primary efficacy endpoints. PGIC will follow the same MMRM that is used for CGIC. EDSS and TNmAS-TL will follow the same MMRM that is used for TNmAS-MAL. Pairwise comparisons between the AERT doses and placebo will be provided at each visit where data are collected. Additional factors (e.g., baseline renal function) along with interaction terms may be included in the models as sensitivity analyses.

10. SAFETY ANALYSES

All Safety analyses will be conducted using the Safety population. All safety analyses will be completed using the actual treatment a subject received (i.e. “as Treated”).

10.1. Adverse Events

The number and percent of subjects with any treatment-emergent adverse events (TEAEs) will be displayed by system organ class and preferred term (MedDRA Version 18.0) for each treatment group. Within each preferred term, subjects will be counted only once if they had more than one event reported during the treatment period.

TEAEs will also be summarized by greatest reported severity for each event preferred term. Counts indicate subjects reporting one or more TEAEs that map to the severity grade classification for each preferred term. At each level of summarization (system organ class or event preferred term) subjects are only counted once and the worst severity case of repeated instances of the same TEAE will be used in tabulations. TEAEs will also be summarized by strongest investigator assessment of relationship to study drug in a similar manner.

Analyses of AEs will be performed for those events that are considered treatment emergent, where treatment emergent is defined as any AE with onset or worsening on or after the first dose of study drug up until 30 days after the last dose of study drug.

Treatment emergent summarization will be characterized by serious or not, the severity and the relationship with the study drug. A conservative approach will be taken to assess the relationship of an AE to study drug; if the relationship of an event is missing, it will be considered treatment-related. Missing severity will be coded as severe.

All TEAEs will be listed individually by subject. In addition, a separate listing will be produced for AEs that are not treatment-emergent.

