7.1.1 Treatment Administration

The study medications will be administered orally twice daily (every 12 hours, or BID) without regard to food.

Dose adjustments, except for those specified in the protocol during the titration and taper periods, are not permitted in this study. Subjects who require a dose adjustment or who discontinue study

drug for greater than 5 consecutive days must be withdrawn from the study and followed for safety ([Section 12.4](#)).

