11.5 Safety Endpoints

Safety endpoints will be reported on the Safety population. Subjects will be reported according to the treatment they actually received. Safety assessment will be based on descriptive statistics and individual subject listings. No statistical tests will be performed for any of the safety assessments.

All reported AEs will be mapped to the Medical Dictionary for Regulatory Activities (MedDRA) system organ classifications (SOCs) and preferred terms (PTs). If a subject reports multiple events of a single PT, the greatest severity and strongest investigator assessment of relationship to study treatment will be assigned to that PT. Summaries of TEAEs will include any AEs reported beginning with the first dose of study treatment on Day 1. The occurrence of TEAEs will be summarized by treatment group using SOCs, PTs, and severity. Separate summaries of treatment-emergent SAEs, TEAEs considered related to study treatment, and events leading to the discontinuation of study drug will be generated.

Descriptive summaries of vital signs, clinical laboratory results, USP results, and the C-SSRS results will be presented by study visit and treatment group. The number and percentage of subjects with treatment-emergent clinical laboratory abnormalities will be summarized by treatment group. Normal range clinical laboratory shifts from baseline to end of study will be summarized by treatment group.

Concomitant medications will be coded using the World Health Organization (WHO) dictionary. These data will be summarized by treatment group. Previous and concomitant medications will be presented in a data listing.

Subject disposition will be presented for all subjects. The numbers of subjects who complete the study and who discontinue early from the study will be provided. The reasons for early discontinuation will also be presented.

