8.6. Treatment Compliance

Dosing information, including date of administration, will be listed by subject.

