1. Impute all non-monotone (intermittent) missing data using the MCMC method of PROC MI. Note that this imputation will sample data within each treatment group. SAS pseudo code is provided below.

2. Using the imputed datasets from Step #1 that are now monotone missing (no intermittent missing data), a single call to PROC MI (including the MNAR statement) will be utilized to impute the monotone missing data. Additional details are provided below.
 - Within the call to PROC MI, one timepoint is imputed at a time. Day 42 first, then Day 84.
 - When imputing at time-point t , the imputation step will include all placebo subjects, but only those from the active arms that have a value missing at time-point t . Subjects with non-missing data that are on active arms will not contribute to the estimation for this step.
 - Repeat the above step for all timepoints t . Thus, the data for timepoint $t+1$ (Day 84) uses the data imputed from previous timepoints (Day 42).

SAS pseudo code is provided below. SAS accomplishes this iterative process in one step. Note that the treatment level 3 is the placebo treatment group:

3. When all missing data are imputed, the MMRM models, as described in Section 9.1.2, will be used to analyze the TNmAS-MAL and CGIC endpoints. PROC MIANALYZE will be used to combine the parameters from the analyses for inference.
 - The above PMM and MMRM analyses will be repeated using only two arms (Placebo and AERT 40 mg). The overall treatment effect could be diluted by the AERT 80 mg dose if there a significant number of discontinuations at this dose level compared to the AERT 40 mg dose, and these analyses serve to compare to Placebo without that possibility. Additionally, this analysis will be completed on Placebo and AERT 80 mg arms, in the unlikely event that there is a trend in the lower dose level causing discontinuations.

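### Adverse events are summarised only as crude subject percentages and time on drug is never tabulated, so later-onset harms at 80 mg would be understated if that arm loses more subjects early

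*SAP*

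**What the plan says.** SAP 10.1 sets the main adverse event summary: "The number and percent of subjects with any treatment-emergent adverse events (TEAEs) will be displayed by system organ class and preferred term". The counting rule is per subject: "Within each preferred term, subjects will be counted only once if they had more than one event reported during the treatment period". SAP 10.2.2 (serious events) and 10.2.3 (events leading to discontinuation or interruption) use the same number-and-percent format. Under SAP 10 these tables use the Safety population as treated.

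An event counts as treatment-emergent under this definition, quoted up to its last word: "any AE with onset or worsening on or after the first dose of study drug up until 30 days after the last dose of study". The window is therefore tied to each subject's own last dose and is shorter for someone who stops early.

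On exposure, SAP 8.6 says only this: "Dosing information, including date of administration, will be listed by subject". SAP 7.4.1 adds that data the plan does not analyse go to listings and not to tables or figures. Protocol 11.5 adds no time-based measure: "Safety assessment will be based on descriptive statistics and individual subject listings".

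Protocol 7.1.1 requires withdrawal of a subject who needs a dose adjustment or is off drug for more than 5 consecutive days. SAP 9.1.3 reruns efficacy models in two arms because the effect could be diluted by 80 mg "if there a significant number of discontinuations at this dose level compared to the AERT 40 mg dose". It adds the reverse analysis "in the unlikely event that there is a trend in the lower dose level causing discontinuations".

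**The concern.** A subject who stops early and has had no event counts as a full non-event in a crude percentage, although that subject was observed for only part of the period in which later harms could appear. If all arms lose subjects alike, the effect on a comparison is small. If one arm loses more, or loses them sooner, its percentages fall relative to the others for reasons unrelated to the drug's risk.

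The SAP recognises that 80 mg is the arm more likely to have this problem and protects the efficacy analysis against it. It does nothing comparable for safety, although safety is part of the primary objective. The comparisons at stake are 80 mg against placebo and against 40 mg, for events that build up over the treatment period. Urinary events are a natural candidate, since Protocol 9.6.2 names a potential urinary risk and monitors it through the study.

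**Working it through.** **What the documents supply.** Treatment lasts 9 + 75 + 7 = 91 days in every arm, and the event window runs 30 days past the last dose. A completer's window is therefore 91 + 30 = 121 days. The documents as available give no dropout rate and no event rate, so there is no plan figure to reproduce.

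**Assumptions for illustration.** Constant hazard; placebo risk 10% over 121 days; 10% placebo dropout with last dose on Day 45; true hazard ratio 1.5 at 80 mg; dropout unrelated to the event; every event in the 30 days after the last dose is captured. Dropout at 80 mg is 20%, 30% or 40%, with last dose on Day 45 or Day 14.

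**Formula.** Crude risk = (1 − d)[1 − exp(−121h)] + d[1 − exp(−(t + 30)h)], where d is the dropout proportion and t the last dose day of dropouts.

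- Placebo: h = −ln(0.9)/121 = 0.000871. Crude risk = 0.9 × 10.0% + 0.1 × 6.3% = 9.6%.
- 80 mg: hazard 1.5h = 0.001306. Full-window risk = 14.6%. Risk in dropouts = 9.3% if t = 45 and 5.6% if t = 14.
- Example, d = 0.3 and t = 45: 0.7 × 14.6% + 0.3 × 9.3% = 13.0%, and 13.0/9.6 = 1.35.

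| 80 mg dropout | Exit Day 45: crude risk, difference, ratio | Exit Day 14: crude risk, difference, ratio |
|---|---|---|
| 20% | 13.6%, +3.9 points, 1.41 | 12.8%, +3.2 points, 1.33 |
| 30% | 13.0%, +3.4 points, 1.35 | 11.9%, +2.3 points, 1.24 |
| 40% | 12.5%, +2.9 points, 1.30 | 11.0%, +1.4 points, 1.14 |

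The reference is full exposure in both arms: 14.6% against 10.0%, a difference of 4.6 points and a risk ratio of 1.46. With 10% dropout at Day 45 in both arms the ratio is still 1.46 (14.1%/9.6%), so the shrinkage comes from differential dropout. Under these assumptions, events divided by person-time recovers the hazard ratio of 1.5 in every row.

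**Effect of onset time.** A second model uses exponential dropout reaching 30% by Day 91 and a true risk of 20% over 91 days. The first figure counts events on drug only; the second adds full capture for 30 days after the last dose.

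| Onset | On drug only | With 30-day capture |
|---|---|---|
| First 14 days | 19.5% | 20.0% |
| Constant hazard | 16.9% | 18.6% |
| Days 42 to 91 | 15.5% | 17.4% |

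At 40% dropout the late-onset figures are 13.9% and 16.4%. The shortfall thus runs from almost nil for early events to about 6 points (20 − 13.9) for late events under heavy dropout with no capture after the last dose.

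**The case against.** The strongest reply is that crude n (%) is a defensible choice in a short trial with the same planned duration in every arm and no safety testing, and that the bias is conditional. Much of this stands.

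- A reader might infer from SAP 9.1.3 that the sponsor forecasts more discontinuations at 80 mg. The text does not say so. It is a conditional rationale for an efficacy sensitivity analysis and gives no rate. It calls a lower-dose trend unlikely, which makes 80 mg the likelier arm but is not a prediction.
- An event that causes withdrawal is already counted, and SAP 10.2.3 gives such events their own table. Early-onset events lose almost nothing.
- It would be too strong to say that attrition is invisible. SAP 8.1 tabulates discontinuations with reasons, and the laboratory, vital sign and USP summaries by time point show falling numbers. These show how many left and roughly when, but they do not give time at risk for adverse events.
- The urinary risk does not rest on crude percentages alone. SAP 10.6 summarises USP scores and changes by time point and arm.
- The 30-day window limits the loss. It does not remove it: under Protocol 9.7.3, events after study completion or withdrawal are reported only if the investigator becomes aware of them.
- SAP 10.6 allows further safety analyses without an amendment. Choosing an exposure adjustment after seeing the arms is weaker than prespecifying it.
- Person-time rates and Kaplan-Meier curves assume non-informative censoring, which may fail here for the same reason that the concern arises. They supplement the crude figures and do not replace them.

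**Conclusion.** The gap is real: no planned table shows time on drug or time at risk by arm, and every planned adverse event summary is a crude subject percentage. The consequence is conditional. If 80 mg loses more subjects early, later-onset events in that arm would be understated and its contrasts reduced. In the illustration, a full-exposure risk ratio of 1.46 falls to between 1.41 and 1.30 with exits at Day 45, and to between 1.33 and 1.14 with exits at Day 14. The Day 14 case is harsh, because it has 80 mg dropouts leaving a month sooner than placebo dropouts, and nothing in the documents supports that timing. All rates are assumed and dropout is taken as independent of the event. The comparison with 40 mg was not computed, but the same mechanism applies.

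A reader might go further and conclude that harms at 80 mg are understated by this plan, or that a signal would vanish. The documents do not support either: they give no dropout or event rates, and the effect depends on differential dropout and late onset together. The change is worth making because it is cheap and because the SAP itself raises the possibility.

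**What to change.** In SAP 8.6, add a by-arm summary of days on double-blind drug (for example mean and median) and total person-days.

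In SAP 10.1, beside the crude n (%), prespecify two measures for any TEAE, serious TEAEs and urinary TEAEs: exposure-adjusted incidence (subjects with a first event per person-time at risk) and Kaplan-Meier time to first event. Both should use the SAP's own window, through 30 days after the last dose, and should not be cut at Day 84, which would drop taper and post-dose events. Keep the crude tables, and keep the additions descriptive in line with Protocol 11.5. State in the SAP that both measures assume non-informative censoring, and that the rate also assumes a constant hazard.

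The cost is a few extra tables built from adverse event onset and dosing dates that the trial already records; SAP 7.3.2.1 already has rules for partial event dates. The drawback is that the added measures rest on assumptions that may fail, so they must be read with the crude figures. No dose, withdrawal or other clinical rule changes.

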10.2. Deaths, Serious Adverse Events and Other Significant Adverse Events

10.2.1. Deaths

All deaths, regardless of causality, will be provided in listings and written clinical narratives.

10.2.2. Serious Adverse Events

The number and percent of subjects with Treatment Emergent Serious Adverse Event (TESAE) will be displayed by system organ class and preferred term, and relationship to study drug, for each treatment group. Within each preferred term, subjects will be counted only once if they had more than one TESAE event reported during the treatment period.

Clinical narratives for each TESAE observed will be written to include important data and safety findings related to the individual TESAE and included in the final clinical study report.

10.2.3. Adverse Events Leading to Discontinuation of Study Drug

The number and percent of subjects with TEAE's leading to discontinuation, or interruption, of study drug will be displayed by system organ class and preferred term for each treatment group. Within each preferred term, subjects will be counted only once if they had more than one TEAE leading to discontinuation, or interruption, of study drug reported during the treatment period.

A listing will be produced for all subjects who reported serious TEAEs or who discontinued study drug due to TEAEs.

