7.9 Treatment Compliance

Subject compliance will be based on drug accountability information. Non-compliance will be defined as subjects taking less than 80% or more than 120% of prescribed study medication as

assessed by the amount of study drug returned by the subject. Dose interruption for more than 5 consecutive days during the titration or maintenance periods will require early study withdrawal of the subject.

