3.3. Summary of Statistical Analysis Changes to the Protocol

The analyses described in this analysis plan are consistent with the analyses described in the study protocol.

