8. SUMMARY OF STUDY DATA

8.1. Subject Disposition

A summary of the analysis sets includes the number and percentage of subjects in each treatment group for the following categories: subjects screened, subjects randomized, subjects in the safety population, subjects in the ITT population, subjects in the mITT population, and subjects in the PP population. All percentages will be based on the number of subjects randomized.

End of trial information will also be summarized in this table, including the number of subjects completing the study and the number of subjects who prematurely discontinued the study with reasons for withdrawal. All percentages will be based on the number of subjects randomized.

A by-subject data listing of study completion information including the reason for premature study withdrawal, if applicable, will be presented.

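### SAP 10.2.3 pools adverse events that only interrupted dosing with those that ended it, so no planned table gives the discontinuation summary promised in Protocol 11.5

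*SAP*

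**What the plan says.** Protocol 11.5 (Safety Endpoints) lists the adverse event outputs. It says that separate summaries of, among others, "events leading to the discontinuation of study drug will be generated". Interruption is not mentioned there.

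SAP 10.2.3 is titled "Adverse Events Leading to Discontinuation of Study Drug". Its table reports counts and percentages for TEAEs "leading to discontinuation, or interruption, of study drug will be displayed by system organ class and preferred term for each treatment group". The counting rule uses the same joined category: within a preferred term, "subjects will be counted only once if they had more than one TEAE leading to discontinuation, or interruption, of study drug". No split of the two outcomes is specified. The section then adds an output with a narrower scope: "A listing will be produced for all subjects who reported serious TEAEs or who discontinued study drug due to TEAEs".

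Three other places bear on the point:
- SAP 3.3: "The analyses described in this analysis plan are consistent with the analyses described in the study protocol".
- SAP 8.1, disposition by treatment group: "the number of subjects who prematurely discontinued the study with reasons for withdrawal". Adverse event is one of the withdrawal reasons in Protocol 12.4.
- Protocol 7.9: "Dose interruption for more than 5 consecutive days during the titration or maintenance periods will require early study withdrawal".

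**The concern.** A table with this title will be read as showing which events made subjects stop treatment. As specified, a subject who paused briefly because of an event and then resumed is counted in the same cell as one who stopped because of it, and the table cannot separate them. That departs from the output promised in the protocol, and SAP 3.3 does not say so.

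Tolerability matters in this trial. Safety is part of the primary objective (Protocol 3.1). Protocol 2.1 names sedation, drowsiness and worsening fatigue as what limits baclofen, and gives improved tolerability as an aim. SAP 9.1.3 allows for more discontinuations at 80 mg than at 40 mg and plans two-arm reanalyses for that case. A reader of the report will therefore want to know which events led to stopping at each dose, and the planned tables do not show it.

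**Working it through.** The documents state no figure on this point, so there is none to reproduce. The check compares the texts and adds arithmetic for scale only.

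**Step 1: promise against specification.** Protocol 11.5 names discontinuation alone. The SAP 10.2.3 title names discontinuation alone. The SAP 10.2.3 table and its counting rule name discontinuation or interruption. The SAP 10.2.3 listing names serious TEAEs or discontinuation, without interruption. Within one SAP section, the title and listing agree with the protocol and the table does not.

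**Step 2: what pooling adds.** Under Protocol 7.9, an interruption of more than 5 consecutive days during titration or maintenance requires withdrawal. In those periods, a subject counted only for interruption has therefore paused for 5 days or less at a time and was not withdrawn under that rule.

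**Step 3: direction within an arm.** For any row, let D be the subjects with an event leading to discontinuation and I those with an event leading to interruption. The table counts D ∪ I, each subject once. D is contained in D ∪ I, so the pooled count is at least the discontinuation count. They are equal only if every subject in I is also in D.

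**Step 4: other outputs.** The disposition table (SAP 8.1) gives withdrawals by reason and arm, without SOC or preferred term. The listing in SAP 10.2.3 is by subject, mixes serious events with discontinuations, and gives no counts by arm. Neither replaces a discontinuation-only SOC and preferred-term table.

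**Step 5: scale.** Planned size is 170 per arm (Protocol 5), so each interruption-only subject adds 1/170 = 0.59 percentage points. Pooled share = discontinuation share + interruption-only share. All rates below are assumed. Discontinuation is held at 5% on placebo and 15% on an active arm (difference 10 points, ratio 15/5 = 3.0).

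| Interruption only, placebo / active | Pooled, placebo / active | Difference | Ratio |
|---|---|---|---|
| 0% / 0% | 5% / 15% | 10 points | 3.00 |
| 2% / 2% | 7% / 17% | 10 points | 2.43 |
| 2% / 5% | 7% / 20% | 13 points | 2.86 |
| 2% / 10% | 7% / 25% | 18 points | 3.57 |
| 5% / 2% | 10% / 17% | 7 points | 1.70 |

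The contrast between arms can rise, fall or stay the same, depending on rates that the documents do not give.

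**The case against.** The strongest reply is that little is lost. Withdrawals for adverse events remain visible by arm in the disposition table. Because a long enough stop forces withdrawal from the study, discontinuing drug for an adverse event and withdrawing for one should largely coincide. The listing identifies the subjects who stopped. The SAP text names both components openly, and a combined count is a legitimate tolerability measure. SAP 7.4.1 allows descriptive categories to be expanded, and SAP 10.6 allows further safety analyses without an amendment. The protocol's vocabulary is also loose: for the same 5-day limit, 7.9 speaks of interruption, while 7.1.1 and 12.4 speak of discontinuing drug. The joined wording in the SAP may simply reflect that.

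Most of this stands, and it limits the point. A reader might infer that the table misstates tolerability by arm, or that the discontinuation rate is lost. The documents support neither. The distortion between arms cannot be sized or signed without interruption rates, the arm-level withdrawal count survives in disposition, and Protocol 11.5 promises a summary of events, not explicitly a rate. A reader might also take Protocol 11.5 to promise permanent discontinuation, but it does not use that word. Nor do the documents show that brief pauses are common or related to dose.

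The reply does not remove the gap itself. The permissive clauses allow a split without requiring one. The loose vocabulary is a reason to define the categories in the SAP. The listing, which leaves interruption out, shows that the SAP itself separates the two outcomes.

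**Conclusion.** The point holds as a reporting inconsistency of minor to moderate severity. Followed as written, SAP 10.2.3 cannot produce the separate summary in Protocol 11.5, and SAP 3.3 does not declare the change. Within an arm the direction is certain: pooled counts equal or exceed discontinuation counts. The amount is unknown, at 0.59 points per interruption-only subject if 170 per arm are analysed. The effect on the contrast between arms is unknown in both size and direction, and is nil if no subject only interrupts. What is missing is the discontinuation-only breakdown by SOC and preferred term. Protocol 11.5 plans no safety tests, so no p-value, error rate or sample size is touched.

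**What to change.** In SAP 10.2.3, tabulate by SOC, preferred term and arm:
- (a) TEAEs leading to discontinuation of study drug, matching Protocol 11.5;
- (b) TEAEs leading to interruption only, as a separate table or column.

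State which eCRF action-taken entry feeds each. Cross-check (a) against the adverse event withdrawal reason in the disposition table, using counts rather than percentages. SAP 8.1 takes percentages of subjects randomized, whereas 10.2.3 uses the Safety population, which requires a dose and a post-dose visit (SAP 7.1.5), so small differences can be legitimate and should be explained. If the sponsor prefers to keep only the joined table, retitle it and record the departure in SAP 3.3.

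The cost is one SAP sentence and one extra table or column, before unblinding, with no new visits or procedures. This assumes that the eCRF distinguishes interruption from discontinuation, which the documents do not show.
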